#### **5.5.4. Patient Characteristics**

The following patient characteristics at baseline will be summarized by treatment group for ITT patients.

- Demographic (age, gender, race and subrace, height, weight, body mass index, Age [ $<20$ ,  $\geq 20$ ])

Note: body weight (as well as BMI) is based on the last observation before Visit 3 injection.

- Baseline MHD category per 30 day ( $<8$ ,  $\geq 8$ ) (Visit 2 to Visit 3) (by ePRO)
- Years since migraine diagnosis
- Migraine and headache related measures (e.g. number of non-MHD with aura, number of migraine headache days with Criteria C), and acute treatment related measures (e.g. number of MHD with triptans use, number of days with triptan use) per 30-day baseline period (Visit 2 to Visit 3) used for secondary and other efficacy measures as listed in
- PGI-S,
- MIDAS (total, each question)
- MSQ (total, 3 sub scores)
- Previous migraine prevention treatment (Yes, No, Yes and did not fail, Yes and fail  $\geq 1$ , Yes and fail  $\geq 2$ ) (Visit 1)
- Number of previous migraine prevention treatment fail (Visit 1)
- Past usage (yes/no) or current usage (yes/no) of followings: Alcohol, caffeine, nicotine replacement therapy, and tobacco and nicotine combined

Note: Except caffeine, summaries are based on patients with  $\geq 20$  years old.

- Medical history (except primary medical conditions). Medical history is defined as illness(es) that ended prior to the signing of informed consent. It will be summarized by preferred term (PT).
- Pre-existing condition (Visit 1). Pre-existing conditions are those AEs existing at Visit 1. It will be summarized by preferred term (PT).
- Number of Comorbid conditions other than migraine. Comorbid conditions other than migraine are those AEs existing before Visit 3 and continuing after Visit 3 other than migraine. (i.e., not contained “migraine” as PT). If it ends on Visit 3, then it is not a comorbid condition. The count is based on PT. (2 events with different LLT but the same PT will be counted as one comorbid condition.)
- Some other baseline variables used for the subgroup analysis in [Table CGAN. 5.8:](#)
  - Having aura or not at baseline (Yes/No) (Visit 2 to Visit 3)
  - Baseline ADA status (Yes/No) (Visit 3)
  - Baseline body weight (weight  $\leq$  median, median  $<$  weight).

Baseline MHD difference by IWRS and ePRO eligibility day will be summarized. Its listing will be created.

Comparisons between treatment groups will be performed using Fisher’s exact test for categorical data and ANOVA with treatment as independent variables in the model for continuous data.

Listing of Subjects Demographic will be created.

#### **5.5.5. Exposure to Investigational Product**

Patients will receive the investigational medicinal product (IMP) at the following planned time points:

- Beginning of Month 1 (Visit 3)
- Beginning of Month 2 (Visit 5)
- Beginning of Month 3 (Visit 6)
- Beginning of Month 4 (Visit 7)
- Beginning of Month 5 (Visit 8)

- Beginning of Month 6 (Visit 10)

The following will be derived from the information recorded on the eCRF:

- For treatment phase (SP III), duration of exposure in days is calculated as treatment phase last visit date – first date IMP administered + 1.
- For treatment phase (SP III), number and percentage of patients with 1, 2, 3, 4, 5, or 6 doses injected.

Comparisons between treatments for duration of IMP exposure will be performed using an ANOVA with treatment in the model. Number of patients with 1 dose, 2, 3, 4, 5 or 6 doses injected will be compared between treatment groups with the Fisher's exact test.

Listing of Subjects with Exposure to Investigational Product will be created.

Listing of treatment exposure with package number and internal lot number will be created.

#### **5.5.6. Treatment Compliance**

Treatment compliance will be calculated for Study Period III as:

$$\frac{\text{number of completed scheduled dosing visits in which the patient received 2 injections} * 100}{\text{number of completed scheduled dosing visits, including any skipped dosing visits before the last dosing visit (Visit 10, inclusive) or early discontinuation visit (exclusive)}}$$

Comparisons between treatments for treatment compliance will be performed using an ANOVA with treatment in the model. For this analysis, a partial dose (for example, a patient only got one injection instead of two) will be considered as no dose received.

#### **5.5.7. Electronic Patient Reported Outcomes Diary Compliance**

Electronic patient reported outcomes diary compliance at each month period and for overall will be calculated:

- SP III: baseline, Month 1, ..., Month 6, overall (Month 1 through Month 6) for ITT population
- SP IV: Month 7, ..., Month 10, overall (Month 7 through Month 10) for post treatment population

Diary compliance at each period is calculated as:

$$\frac{\text{Actual number of diary days in the period}}{\text{Expected number of diary days in the period}} * 100$$

Expected number of Diary days for baseline is calculated as date when a patient becomes eligible day minus date of Visit 2+1 (diary for Visit 2, diary for Visit 2+1, ..., diary for eligible day).

For each patient, overall diary compliance for SP III is average of monthly compliance in SP III (Month 1, ..., Month 6). If he discontinues early, then ignore the rest of the month. In this case, the last month compliance is based on  $\max(30, \text{the total number of calendar days in that month})$  (See Section 5.4.1)

Expected number of Diary days for Month 7, Month 8, Month 9, and Month 10 in SP IV is calculated similarly. Note that 2-month visit interval (e.g. Month 7 and Month 8) will be split into two one-month interval as defined in Section 5.4.1. The section explains how to handle early discontinuation case.

For each patient, overall diary compliance for SP IV is average of monthly compliance in SP IV (Month 7, ..., Month 10). If he discontinues early, then ignore the rest of the month. In this case, the last month compliance is based on  $\max(30, \text{the total number of calendar days in that month})$  (See Section 5.4.1)

Example: Expected number of diary days in the period Month 3 = date of Visit 7 – date of Visit 6 (diary for Visit 6, diary for Visit 6+1 day, ..., diary for Visit 7-1 day.)

In addition following will be summarized for each month and for overall:

- subjects with  $\geq 80\%$  compliance
- subjects with  $\geq 50\%$  compliance

Treatment comparisons for diary compliance for each month and for overall will be performed separately using an ANOVA with treatment in the model.

### **5.5.8. Previous Migraine Prevention Therapy and Previous Migraine Acute Treatment**

The proportion of patients who received previous migraine prevention therapy, and the proportion of patients with response to the previous migraine prevention therapy within each of the 6 categories (to enter this trial, medical history event, adequate response, inadequate response, no response, and treatment availability) will be summarized for ITT patients.

Treatment group comparisons will be done using the Fisher's exact test.

Previous migraine prevention therapies are migraine prevention therapies that started prior to the date of the first injection and stopped prior to or at the date of first injection which has indication recorded in the CRF (prior therapy migraine medication, or concomitant medication) as one of the followings:

[1] "primary study condition" (except acute treatment)

[2] corresponding medical history event (preferred term) that includes "migraine" (except acute treatment)

[3] corresponding adverse event (preferred term) that includes “migraine” (except acute treatment)

Note that all records in the prior therapy migraine medication CRF have the indication “primary study condition”.

Previous migraine prevention therapy and migraine prevention therapy during SP III and SP IV (Section 5.5.9) will be reviewed by medical to exclude non-migraine prevention therapy before DBL.

Previous migraine acute treatment during SP II will be summarized by following categories (can be multiple classes):

- triptans,
- NSAIDs/aspirin,
- acetaminophen/paracetamol,
- ergots,
- anti-nausea
- Chinese medicine
- Others

Previous migraine acute treatment are migraine acute treatment used in during SP II. Migraine acute treatments will be identified either by eDiary or by the concomitant medication CRF with one of the following indications:

[1] “primary study condition” (except migraine prevention therapies)

[2] corresponding medical history event (preferred term) that includes “migraine” (except migraine prevention therapies)

[3] corresponding adverse event (preferred term) that includes “migraine” (except migraine prevention therapies)

Previous migraine acute treatment and migraine acute treatment during SP III and SP IV (Section 5.5.9) will be reviewed by medical to exclude non-acute treatment and to categorize them into the above definitions before DBL.

Regarding migraine acute treatment (and previous migraine acute treatment), combination medications (such as aspirin/acetaminophen/caffeine) will be counted in each medication category that applies (such as NSAIDs/aspirin and Acetaminophen/paracetamol).

### **5.5.9. Concomitant Therapy, Migraine Prevention Therapy, and Migraine Acute Treatment.**

The proportion of patients who received concomitant medication will be summarized for ITT population for Study Period III and for the post-treatment population for Study Period IV separately. The concomitant therapy does not include migraine acute (abortive) treatments or migraine prevention therapy.

Concomitant therapies for study period III are those which started, stopped or continued in study period III. If medication started and stopped on the same day of injection, it will still be considered as concomitant medication for SP III. If medication started before the first day of injection but stopped on the same day of injection, then it will not be counted as concomitant medication for SP III.

Concomitant therapies for study period IV are those which either started, stopped or continued in Study Period IV. If medication started and stopped on the first day of SP IV, it will still be considered as concomitant medication for SP IV.

Treatment group comparisons will be done using the Fisher's exact test for Study Period III with ITT population. Descriptive statistics only will be presented for the treatment groups in Study Period IV with the post-treatment population.

Similar outputs for migraine prevention therapy will be created for SP III and SP IV. As mentioned in the previous section, the definition of the prevention therapy will be reviewed by medical before DBL.

Similar outputs for migraine acute treatment will be created for SP III and SP IV separately. The categorization is based on Section 5.5.8.

## **5.5.10. Efficacy Analyses**

### **5.5.10.1. Primary Outcome and Methodology**

The primary efficacy objective is to assess whether at least 1 dose of LY2951742 (120 or 240 mg/month) is superior to placebo in the prevention of migraine headache in patients with episodic migraine.

The primary analysis will evaluate the efficacy of LY2951742 (120, or 240 mg/month) compared with placebo on the overall mean change from baseline in the number of monthly migraine headache days during the 6-month treatment phase.

The primary analyses will be performed using a REML-based MMRM technique. The analysis will include the fixed categorical effects of treatment, month, and treatment-by-month interaction, as well as the continuous fixed covariates of baseline number of migraine headache days and baseline-by-month interaction.

An unstructured covariance structure will be used to model the within-patient errors. The Kenward-Roger (Kenward and Roger 1997) approximation will be used to estimate denominator degrees of freedom. If the model does not converge, the Fisher scoring algorithm will be implemented by specifying the SCORING option (SCORING=5) in SAS. If the model still fails to converge, the model will be fit using covariance matrices of the following order specified by a decreasing number of covariance parameters until convergence is met:

- Heterogeneous Toeplitz = toeph
- Heterogeneous First-order autoregressive = arh(1)
- Toeplitz = toep
- First-order autoregressive = ar(1)

Hence we fit the model by the following order:

- [1] unstructured covariance with the default fitting,
- [2] unstructured covariate with the Fisher scoring,
- [3] toeph covariance with the default fitting,
- [4] toeph covariance with the Fisher scoring
- [5] arh(1) covariance with the default fitting,
- [6] arh(1) covariance with the Fisher scoring
- [7] toep covariance with the default fitting,
- [8] toep covariance with the Fisher scoring
- [9] ar(1) covariance with the default fitting,
- [10] ar(1) covariance with the Fisher scoring

When the unstructured covariance matrix is not utilized, the sandwich estimator (Diggle and Kenward 1994) will be used to estimate the standard errors of the fixed effects parameters. The sandwich estimator is implemented by specifying the EMPIRICAL option in SAS®. When the sandwich estimator is utilized, the Kenward-Roger approximation for denominator degrees of freedom cannot be used. Instead, the denominator degrees of freedom will be partitioned into between-subject and within-subject portions by the DDFM=BETWITHIN (DDFM=BW) option in SAS®. If the model is still non-convergence, then baseline-by-month interaction may be excluded from the model.

The primary endpoint of this study for each LY2951742 dose arm compared with placebo will be estimated as the main effect of treatment from the MMRM analysis during the 6-month treatment phase. This provides the average treatment effect across 6 months of double-blind treatment phase. The repeated-measures analysis will include data from all 3 treatment groups. The Type I error rate for the study will be controlled at a 2-sided 0.05 level (equivalently, one-sided 0.025 level). For the multiplicity adjusted p-value calculation for the primary endpoint, the pairwise treatment effect comparisons of each dose of LY2951742 versus placebo will be conducted using the Step-down version of Dunnett' s procedure.

To implement the multiplicity adjustment, SAS® PROC GLIMMIX (with dist=normal option and residual option) will be used with the "adjust=dunnett stepdown" option. When the model is

fit with unstructured covariance, “adjust=dunnett stepdown ADJDFE=ROW” option will be used to adjust denominator degrees of freedom. The adjusted p-values will be reported for both LY arms (control arm is placebo).

The primary analysis will be also performed without multiplicity adjustment by SAS® PROC MIXED. This is mainly to show point estimators at each month and associated 95% confidence intervals.

The results of the statistical tests (by SAS® PROC MIXED) at each month in the double-blinded treatment phase from the primary analysis model will be used to assess the onset of effect for each LY2951742 dose arm compared with Placebo. In particular, if the primary efficacy analysis is statistically significant (with multiplicity adjustment), then the earliest month when statistical significance (without multiplicity adjustment) is observed and maintained for all the subsequent months during double-blinded treatment phase will be considered as the onset of effect.

The primary efficacy result (by SAS® PROC MIXED) will be plotted by each treatment arm (horizontal axis= month, vertical axis = change from baseline).

Effect size for change in migraine headache days (primary analysis) and number needed to treat for 50%, 75% and 100% response rate (key secondary analysis) will be created (time point=overall during 6 month double blind period) .

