To avoid biased reporting, patients must not be told the number of migraine headache days on which study qualification is based.

Study Period III: At the start of the 6-month, double-blind treatment phase (Visit 3), patients meeting all eligibility requirements will be randomized to 1 of 3 treatment groups in a 2:1:1 ratio to receive placebo, 120 mg/month galcanezumab, or 240 mg/month galcanezumab, respectively.

Patients randomized to the 120 mg dose of galcanezumab will receive an initial loading dose of 240 mg (2 injections of 120 mg each at Visit 3 only). To preserve blinding throughout the study, patients in all treatment groups will receive 2 injections of investigational product at each dosing visit. At Visit 3, if available and where local regulations in Japan and ethical review boards/institutional review boards (ERBs/IRBs) allow, patients will also watch a training video designed to address patient expectations with regard to participation in a placebo-controlled trial, and the difference between medical treatment and research.

The patient will be considered enrolled in the study when randomization occurs. During this phase, study procedures at dosing visits must always occur prior to the patient receiving his/her assigned treatment of study drug.

Patients will be given injections of study drug during office visits ([Figure CGAN.5.1](#)). For all treatment groups, subcutaneous injections will be administered once monthly at the dosing visits. At Visit 3 (first dose), patients will be required to remain at the site for observation for at least 30 minutes post-injection. Following subsequent doses, patients will be observed for at least 30 minutes post-injection if they have a significant adverse event after the first injection and/or they are judged by the investigator to have risk of a significant adverse event after injection. Patients will continue to log in and complete the ePRO diary each day. Patients may continue to take their allowed acute migraine headache medication (with some limitations; see concomitant medication study tool) during the treatment phase.

Patients who do not participate in the CGAP study and who complete Study Period III, or who discontinue for any reason during Study Period III, will be expected to enter post-treatment follow-up (Study Period IV).

Patients who discontinue for any reason during Study Period III will be expected to take the measurement for Early Termination (ET).

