7.1.1. Packaging and Labeling

Galcanezumab and matching placebo (excipients only) will be supplied as an injectable solution in 1-mL, single-dose, prefilled, disposable, manual syringes with study-specific labels. Each syringe of galcanezumab is designed to deliver galcanezumab 120 mg. The syringes (and contents), containing either galcanezumab or placebo, will be visibly indistinguishable from each other. Syringes will be supplied in cartons, with the appropriate quantity of syringes specific to the planned dispensing schedule of investigational product.

Clinical trial materials will be labeled according to the Japanese regulatory requirements.

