7.3. Blinding

This is a double-blind study. To preserve blinding throughout the study, patients in all treatment groups will receive 2 injections of investigational product at each dosing visit.

To preserve the blinding of the study, a minimum number of Lilly personnel will see the randomization table and treatment assignments before the study is complete.

Emergency unblinding for AEs may be performed through the IWRS. This option may be used ONLY if the patient's well-being requires knowledge of the patient's treatment assignment. All unblinding events are recorded and reported by the IWRS.

If an investigator, site personnel performing assessments, or patient is unblinded, the patient must be discontinued from the study. In cases where there are ethical reasons to have the patient remain in the study, the investigator must obtain specific approval from a Lilly clinical research physician (CRP) or clinical research scientist (CRS) for the patient to continue in the study.

In case of an emergency, the investigator has the sole responsibility for determining if unblinding of a patient's treatment assignment is warranted. Patient safety must always be the first consideration in making such a determination. If the investigator decides that unblinding is warranted, the investigator should make every effort to contact the Lilly CRP/CRS prior to unblinding a patient's treatment assignment, unless this could delay emergency treatment of the patient. If a patient's treatment assignment is unblinded, Lilly must be notified immediately.

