**Primary Measure: the Number of Monthly Migraine Headache Days**

The primary measure is the number of monthly migraine headache days. A migraine headache day is defined as a calendar day on which a **migraine or probable migraine** occurs.

The primary measure of the number of monthly migraine headache days will be summarized from the daily ePRO data for each patient in that period (including 30 days of daily data from the baseline period prior to randomization, 6 months of daily data during the treatment phase, and 4 months of daily data during the post-treatment phase).

The daily data will be aggregated, and the number of migraine headache days will be provided for each of the 30-day periods. In calculating the number of migraine headache days for each period, if the period is not equal to 30 days, the number of migraine headache days will be normalized by multiplying the number of migraine headache days by  $(30/x)$  where 'x' is the total number of non-missing diary days in the period.

For the baseline period (Visit 2 to Visit 3), once a patient becomes eligible before Visit 3 judged from the daily ePRO data (this is called **eligible day**), then all ePRO data after the eligible day to Visit 3 will be ignored.

Example: A patient has Visit 2 = 2016/Jan/1. He records diary on Jan/2 for his headache information on Jan/1. He records diary everyday (no missing data.) He records diary on Jan/31 for his headache information on Jan/30 which ends up as 5th migraine headache day during the baseline period (starting from Jan/1.) He becomes eligible for CGAN study (assuming all other eligibility conditions are met.) He goes to a site on Feb/ 4 (Visit 3) and gets 1st injection on the day. In this case **eligible day** is 2016/Jan/30. All diary data of Jan/1, Jan/2,..., Jan/30 will be used as baseline period data. All diary data of Jan/31, Feb/1, Feb/2, Feb/3 will be ignored. Diary data on Feb/4 (Visit 3) is used for Month 1 period data.

For the double blind period (SP III), Month 1 period data is based on headache information from Visit 3 up to on Visit 5 – 1 day. Month 2 period data is based on headache information from Visit 5 up to Visit 6 – 1 day. Month 3, to Month 6 will be defined similarly.

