For visitwise indicators of 50% responders, the results of the statistical tests at each month in the double-blinded treatment phase from categorical MMRM analysis (PROC GLIMMIX) will be used to assess the onset of 50% sustained response for LY2951742 compared to Placebo. In particular, if the key secondary measure of 50% response rate is statistically significant, then the earliest month where the statistical significance is observed and maintained for all the subsequent months during double-blinded treatment phase will be considered as the onset of 50% sustained response.

For non-repeated binary measures, such as 50% response sustained for three consecutive months until patient's endpoint in 6-month treatment phase and 50% response sustained from month 1 to

month 6, a logistic regression analysis with covariates of treatment and baseline will be conducted.

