#### **Analyses for Number of Weekly Migraine Headache Days in Month 1**

The number of weekly migraine headache days in Month 1 can be considered as ordinal data with possible values of 0, 1, 2, 3, 4, etc. (Note: week 4 may have more than 7 migraine headache days because of the definition. If duration of Visit 3 to Visit 5 is 31 days, then duration of week 4 is 10 days with day 22, day 23, ..., day31) It will be analyzed using an ordinal repeated measures model implemented using the GLIMMIX procedure in SAS. In this model, a proportional odds model with cumulative logit link will be used, and a random intercept will be applied to the observations for each patient to account for repeated measures. The model will include the fixed, categorical effects of treatment, week, and treatment-by-week interaction, as well as the continuous, fixed covariate of baseline number of migraine headache days (/month) and baseline number of migraine headache days by week interaction. Log (number of compliant calendar days within each week/7) will be used as the offset in the model.

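### Both galcanezumab arms receive the same 240 mg throughout Month 1, so a difference between them in the Month 1 test or weekly Month 1 result can only be chance, and testing each arm alone leaves a third of the Month 1 information unused

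*SAP*

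**What the plan says.** Protocol 5.1 states that patients in the 120-mg arm "will receive an initial loading dose of 240 mg (2 injections of 120 mg each at Visit 3 only"). Under Protocol 7.3, "patients in all treatment groups will receive 2 injections of investigational product at each dosing visit", and under 7.1.1, "Each syringe of galcanezumab is designed to deliver galcanezumab 120 mg". The 240-mg arm therefore also receives two 120-mg syringes at Visit 3.

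SAP 5.5.5 places the second dose at Visit 5, the start of Month 2. SAP 5.4.1 says "Month 1 period data is based on headache information from Visit 3 up to on Visit 5", less one day, so Month 1 ends before the regimens separate.

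The monthly tests "will be used to assess the onset of effect for each LY2951742 dose arm compared with Placebo" (SAP 5.5.10.1). If the multiplicity-adjusted primary result is significant, onset is the earliest month with unadjusted significance that then holds in every later month. SAP 5.5.10.3 uses the monthly response-rate tests in the same way to assess "the onset of 50% sustained response for LY2951742 compared to Placebo"; that sentence does not itself name the arms. For the weekly Month 1 analysis, "The model will include the fixed, categorical effects of treatment, week, and treatment-by-week interaction". SAP 5.5.1 defines a combined arm, LY_All, only for summary displays. No pooled Month 1 efficacy contrast is planned.

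The SAP does recognise the shared first dose elsewhere. In Example 1 under the Safety Population (5.5.1.3), a patient randomised to 120 mg who stops after the loading dose is counted in the 240-mg group.

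**The concern.** Protocol 5.5 justifies the loading dose by the finding that a dose above 120 mg separated from placebo as early as Month 1. The matching question in this trial is whether a 240-mg first dose works in Month 1. About 226 patients receive that first dose, but the plan answers the question twice, with 113 patients each time.

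Two things are at stake. One is precision: a real but modest Month 1 effect is more likely to be missed. The other is interpretation: if one arm reaches significance at Month 1 and the other does not, a reader will be inclined to see a dose effect where the two arms had received the same treatment. Onset of effect and onset of sustained 50% response are both listed secondary objectives (Protocol Table CGAN.4.1, SAP Table CGAN.4.2).

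**Working it through.** **Inputs.** Arm sizes of 225, 113 and 113, effect size 0.36, 15% discontinuation and power of about 88% come from Protocol 10.1 and SAP 5.2. Effects are in standard deviation units.

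**The plan's own figure.** Take completers of 191, 96 and 96 (85% of each arm), an effect of 0.36 in both doses, and the two-sided Dunnett test with correlation 0.334 (critical value 2.227). By simulation the power for at least one dose is 89.6%, within two points of the stated 88%. Without dropout it is 93.8%; with the effect in one dose only it is 75.1%. The stated power is reproduced and is not in question.

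**Month 1 precision.** Assume equal variances and ignore dropout, which should be small in the first month.

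- One arm versus placebo: variance = 1/113 + 1/225 = 0.01329; SE = 0.1153.
- Both arms versus placebo: variance = 1/226 + 1/225 = 0.00887; SE = 0.0942.
- Variance ratio = 0.00887/0.01329 = 0.667, so a per-arm comparison carries one third less information.
- SE ratio = 0.0942/0.1153 = 0.817, so pooling cuts the SE by 18%.

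**Power of the Month 1 test.** Power is Φ(effect/SE − 1.96). At 0.25, per arm: 0.25/0.1153 = 2.168, giving 58%. Pooled: 0.25/0.0942 = 2.655, giving 76%.

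**Chance disagreement.** The two arm statistics share the placebo group, so their correlation is (1/225)/0.01329 = 0.334. With identical true effects, the probability that exactly one arm is significant is 2 × (power per arm − probability both are significant). At 0.25 this is 2 × (0.583 − 0.392) = 0.38.

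| Assumed Month 1 effect | Power per arm | Power pooled | Exactly one arm significant |
|---|---|---|---|
| 0.25 | 58% | 76% | 38% |
| 0.30 | 74% | 89% | 31% |
| 0.36 | 88% | 97% | 18% |
| 0.50 | 99% | about 100% | 2% |

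**From the Month 1 test to declared onset.** The last column is disagreement in the Month 1 test only. Declared onset also needs Months 2 to 6. The SAP rule was therefore simulated with no dropout, the primary-result condition not applied, and an assumed within-patient correlation of 0.4 to 0.8.

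- Month 1 effect 0.36 in both arms, later effects 0.25 (120 mg) and 0.45 (240 mg): among trials in which only one arm has onset at Month 1, 80% to 86% have both arms significant at Month 1. The disagreement comes from the later months.
- Trials in which both doses stay significant throughout Months 2 to 6: any difference in Month 1 onset then comes from the Month 1 test and is chance. It occurs in 31% to 38% of such trials if the Month 1 effect is 0.25 (later effects 0.36 to 0.50), and in 3% to 9% if the effect is 0.36 in every month.

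**The case against.** A reader might go further and infer that any dose difference in onset at Month 1 must be chance. The documents do not support that. Onset in SAP 5.5.10.1 is not the Month 1 test alone: it needs a significant primary result and significance in every later month, and the doses differ from Visit 5. A lower dose that fails to hold significance can have a later onset for a real reason. This part of the objection stands in full.

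A second objection is that per-dose comparison with placebo is the stated aim (Protocol Table CGAN.4.1, SAP 4.2.2), that each test is a valid randomised comparison of a regimen including its loading dose, and that no 120-mg versus 240-mg comparison of onset is planned. This also stands. It argues against removing the dose-specific rule, not against adding a pooled estimate.

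A third is that putting a pooled Month 1 test inside the onset rule would often achieve little. With equal effects of 0.36 in all months, disagreement in declared Month 1 onset falls only from 39.8%, 36.3% and 31.4% (correlation 0.4, 0.6, 0.8) to 37.3%, 34.0% and 29.5%, because most of it comes from demanding repeated significance in each arm. With later effects of 0.25 and 0.45 and correlation 0.4, it rises from 65.8% to 69.6%. The gain is large only when the Month 1 effect is modest and later effects are strong: with 0.25 at Month 1 and 0.50 later in both arms, it falls from about 38% to 3% or less. Replacing the rule is therefore not proposed.

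Finally, onset is an other secondary objective without multiplicity control, and monthly estimates by arm will be shown with 95% confidence intervals. That limits the consequence but does not recover the unused precision.

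**Conclusion.** The point holds as one of precision and interpretation, not of type I error. Treatment in the two active arms is identical throughout Month 1, so a difference between them in the Month 1 test, or in the weekly Month 1 analysis, can only be chance. The weekly analysis has no maintenance rule, so there the point applies without qualification. Per-arm testing leaves one third of the Month 1 information unused on the inverse-variance scale, or 18% on the standard-error scale. The primary analysis and its Dunnett control are unaffected.

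The practical size depends on the Month 1 effect: considerable at 0.25 (power 58% against 76%), negligible at 0.50. The range 0.25 to 0.50 is an assumption. The documents give 0.36 only in the study's power calculation, not for Month 1. The precision ratio needs no effect size; it rests on the planned arm sizes, equal variances and little dropout in the first month. It is exact for the simple difference in means used here and approximate for the response-rate and weekly models.

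**What to change.** - In SAP 5.5.10.1 and 5.5.10.3, add a prespecified pooled Month 1 contrast (mean of the two active arms versus placebo) to the existing MMRM and GLIMMIX models, as the estimate of the Month 1 effect of the 240-mg first dose. Settle it before the interim database lock, which is when the treatment-period results become final.
- In the weekly Month 1 model, code treatment as active versus placebo, and tabulate the by-arm results alongside.
- Keep the dose-specific onset rule, and report it beside the pooled Month 1 result.
- State that Month 1 treatment was identical in the two active arms, so that a dose difference in onset arising only from the Month 1 test is not to be read as a dose effect.

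The cost is one extra contrast per model and a two-level treatment variable in the weekly model. The weekly test is then no longer dose-specific, but the design gives no dose contrast in that month to lose.
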